## **6. Potential Risks/Discomforts to Study Participants**

Activities during the first phase of the study do not involve human subject research. The studies in phases 2 and 3 pose very low risks to study participants. The involvement of the participating organizations' administrators and interventionists in training is much in the nature of a quality improvement project; they are openly engaged in a process designed to refine the Savvy interventionist training system, so there are no threats to confidentiality or other forms of injury or harm. For the caregivers involved in the studies, the two main possible risks are to confidentiality and to minor emotional upset that might occur in answering study questions.

Based on prior experience with Savvy Caregiver program research and its implementation in community agencies, we cannot identify any expected serious adverse effects – as defined in the NIA Adverse Event and Serious Adverse Event Guidelines – that might occur to phase 2 and 3 caregiver study participants. Likewise, we cannot identify any expected serious adverse events occurring to those who are trained to become Savvy interventionists or those who administer the organizations within which Savvy is offered.

## **7. Potential Benefits**

For the participating organizations and interventionists, the main potential benefit will be the addition of a capacity for serving clients. The organization will be able to offer an evidence-based program (Savvy), and the interventionist will acquire a new skill. More broadly, the system will be poised to extend the capacity of a wide range of other organizations to offer Savvy. For caregivers who take part in the phase 2 or phase 3 study, they will all have the opportunity to take part in the Savvy Caregiver program, a program that has repeatedly

demonstrated positive outcomes in the areas of caregiver well-being and caregiving competence. But caregivers may or not receive any benefit to taking part in the study.

## **8. Compensation**

Caregiver study participants will receive a \$25 honorarium in the form of a gift card following each data collection event. The gift cards will be sent by mail.

## **9. Data Analysis: Data Management and Monitoring**

Data Collection and Management. Emory study staff will use an IRB-approved phone or video consent process to enroll individuals from the three groups that are targets for our formative evaluation activities, and study staff and team members will gather data from them in the ways described below:

### **Data Collection**

*Interventionists.* We will conduct three recorded semi-structured video interviews with each interventionist. One will occur immediately after training; this will focus on their sense of the completeness and adequacy of the training program, including the training methods, videos, and materials, and their perceived readiness to lead the program. We will also interview them immediately after the conduct of each of the two Savvy programs they lead, asking them to report on their own performance as interventionists, including any adaptation processes in which they might have engaged, and to reflect on ways the training might be improved to strengthen their skills, including for adaptation. In total: 18 interviews.

*Savvy Participants.* Using an on-line survey method, we will ask each caregiver to complete the post-program fidelity monitoring survey (see Appendix) that seeks responses to the program (feel more knowledgeable, more competent, better equipped, etc.) and asks them to assess the interventionist's performance and verify that certain key elements of the program were covered (N=36; 6 in 6 groups). We will also conduct recorded semi-structured video interviews with a small sample of participants (N=8-12), selected to achieve maximum variability of relationship to care recipients, gender, racial/ethnic heritage, and rating of the program and the interventionists. Interviews will focus on caregivers' perceptions of the interventionist's program leadership skills, any adaptation experiences, and on ways in which they met their own needs and expectations.

*Organizational Leaders.* We will conduct recorded semi-structured video interviews with sponsoring organizations' key contact persons immediately after the interventionist training and then after each of two Savvy offerings. The conversation will focus on identifying ways to strengthen and improve the training, certification, and fidelity monitoring system. We will also seek information about time and resource costs of the program, caregiver demand, and caregiver recruitment and feedback (3 interviews per organization).

Results from Savvy participant quantitative fidelity monitoring surveys will be compiled in a simple spread sheet to allow us to see whether there are any notable problems in interventionist performance either within or across sites or in or across interventionists. Likewise, we will be able to compare caregivers' responses about knowledgeability and competence with responses we have received from other caregivers in Savvy programs provided by interventionists who were trained in person by [name] or [name].

## **Data Management**

Data will be entered at the time of each interview directly into the dedicated project tablet computer and saved on Emory's secure REDCap platform. All data entry screens are set up in REDCap and, where possible, include data delimiters (i.e., skip patterns, valid range limits) to ensure correctness and minimize missing data. Data will be exported weekly and analyzed for data cleaning and verification. Upon completion of each cohort data-gathering point, all data will be merged for scale computation, aggregation, and analysis. In preliminary analyses, descriptive statistics and frequency distributions will be examined to identify outliers and ensure integrity of merged files. For all multi-item scales, internal consistency will be examined using Cronbach's alpha and associated statistics (e.g., item-total correlations, alpha if item deleted).

Preliminary analyses will examine baseline differences among completers and non-completers and by study arm (immediate/delayed) as a randomization check using 2-group comparison tests (t-tests and non-parametric equivalent tests for continuous variables (normally or non-normally distributed) and Chi-Square tests for categorical variables). The association of predisposing factors (demographics, CG history, relationship and care recipient status at baseline) at baseline data with changes in outcomes over time will be examined to identify significant covariates. Where significant associations with baseline measures are detected, these potential confounders will be controlled for in subsequent analyses using covariate model adjustments.

## **Monitoring**

The School of Nursing at Emory University will maintain close contact with every entity within the study and will monitor study activities. We will use a common study web-portal using the Research Electronic Data Capture (REDCap) created and managed in Emory SON. We will create and update study participants' data through REDCap. During data entry, automated checks will be performed that will immediately flag problematic data (e.g., missing, out of range, inconsistent), allowing for the research staff member to address any discrepant data promptly thus increasing data quality. Data entered into the web-based form are immediately stored in a study database and tracked through a journaling process where they are accessible for review by the study team. Suspicious data can be flagged through a query management system, and automated alerts provided to the sites. A complete audit trail is stored for each database modification. Any discrepant data identified through analytic manipulations will be communicated to the sites. Once all queries have been resolved and the database has been deemed "clean", it will be officially locked. All permissions to make changes (append, delete, modify or update) to the database will be removed at that time.

Record keeping and data collection are the responsibilities of the research staff under the supervision of the PI. The investigator is responsible for ensuring the accuracy, completeness, legibility (if hardcopies of worksheets are used), and timeliness of the data reported.

All study's written records will be stored in a locked cabinet for 5 years. Study data will be de-identified and shared with future researchers per written request and IRB approval (Resource and Data Sharing Plans).

## **10. Plans for analysis**

Multi-level mixed effects models (MLM) with random (participant) and fixed (cohort) effects will be employed to test for linear (and non-linear) trajectories of change for the Intervention group versus waitlist

group focusing on the group-by-time effect. To address the primary effect of the Savvy intervention, the Immediate group will be compared to the waitlist delay group, using the first 2 time points (0m-2m) to test for differences between the 2 groups' changes post intervention. Additionally, the combined Savvy intervention effects will be assessed using a paired t-test for the combined immediate group's first 2 time points (0m-2m) with the waitlist delay group's 2 time points before and after beginning Savvy (4m-6m). If there are significant differences between the 2 groups at the time point immediately prior to receipt of the intervention, these "baseline" effects will be included and adjusted for a final analysis of covariance (ANCOVA) model for these change scores. Given that the immediate group will have 3 post-intervention measurements (2m-4m-6m), MLM longitudinal models will also be employed to assess the overall time effects plus planned post hoc comparisons for both the immediate intervention effect and the longer term and sustained effects. Sidak Type-I error rate adjustment (which has higher power than Bonferroni) will be applied for the multiple pairwise time point comparisons. The proposed study design also has the advantage of capturing "baseline" time points for the delay group (0m-2m-4m) which will provide an excellent opportunity to evaluate what if any potential "placebo" effects there may be from being enrolled in this type of study. These initial data captured at 0m-2m-4m for the delay group will also be used to evaluate any potential decline occurring during this time period. All model assumptions will be tested; grand mean centering used to help combat multi-collinearity between variables; and standard diagnostic tests and influence statistics used to test the distributions of the residuals. MLM models utilize all available data for all participants at each time point and have the advantage of adjusting for the missing data over time, where repeated measures ANOVAs do not. Further covariate predictors of missingness (mainly due to attrition) over time will be included to additionally adjust for these confounders SPSS v.24 will be used for all analyses at the 5% significance level.

We will use a meta inference process to answer the central question of this project: Can the system train interventionists to maintain fidelity to core SAVVY principles and demonstrate the ability to tailor the implementation to match cultural values of the community? This inference procedure examines both the process (System Effectiveness Study) and the outcomes (preliminary Efficacy Study). The research team will follow a series of analytic steps to create meaning out of the relatively large amount of collected data, incorporating both the quantitative and qualitative components in a dynamic and interactive manner. We will look first at the results interventionists' ability to provide Savvy faithfully and in a manner congruent with local values: What conclusions or trends do fidelity monitoring, caregiver surveys, and interviews with all parties yield? Next we examine the impact of Savvy on participating caregivers to further establish the effectiveness of the system. If caregiver outcomes improve, this will provide a demonstration that system-trained interventionists can faithfully deliver Savvy in such a manner that its mechanism of action can have an expected effect on caregiver participants. If the outcomes do not support the effectiveness of this new system on either or both questions, we have the data to inform further system development work. The outcome of this process will be a finalized interventionist training system, one informed by a contextual understanding of the effects of the system and ready for a next step, a Stage III or IV intervention trial.

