#### **4. Goals/Aims**

*Aim 1.* Develop a prototype web-based system for Savvy interventionist training and certification and an accompanying performance fidelity monitoring process. Development efforts will yield web-based components delivered through freely available course management and survey applications (e.g., Canvas; Articulate Rise) that will enable sponsoring entities to train and certify interventionists who can locally tailor Savvy, monitor the fidelity of their performance in delivering Savvy, and assess the program's impact on caregivers.

*Aim 2.* Establish the field-readiness of the system. We will engage three community entities serving culturally, ethnically, and geographically diverse constituencies to collaborate with the study team and expert advisory panel in a highly participatory formative test of the prototype system developed through Aim 1 activities. Results and feedback will inform finalization of materials for the Aim 3 trial.

*Aim 3.* Conduct a field trial of the system. The trial will test the effectiveness of the system and examine its preliminary efficacy in producing expected outcomes (i.e. well-being, mastery) in a diverse group of caregivers participating in programs delivered by newly trained interventionists. Six culturally or organizationally diverse sponsors will recruit 2 individuals each to be trained as Savvy interventionists (12 interventionists) and each sponsor will then recruit at least 20 caregivers to take part in a wait-list, no control group study (N=120) of the performance of the interventionists and the preliminary efficacy of the Savvy program provided by them.

The figure below provides a broad timeline for project activities. While we will begin some Aim 2 activities before all of the Aim 1 activities are complete and some Aim 3 activities before all of the Aim 2 activities are complete, we expect Aim 1 activities to be complete by project month 12 and Aim 2 activities to be complete by the end of the second project year.

		Year 1	Year 2	Year 3	Year 4
Project startup activities	Project startup activities	Start			
	Preliminary Syllabus & Materials	Start	End		
	Storyboard Content & Delivery		Start		
	Materials Production		Start		
Recruit/orient 3 organizations	Recruit/orient 3 organizations				
	Train interventionists		Start		
	Interventionists provide Savvy		Start		
	Evaluate & revise		Start		
Recruit 6 organizations	Recruit 6 organizations				
	Train interventionists			Start	

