## **Field Methods**

**Data Collection and Management.** Emory study staff will use an IRB-approved phone or video consent process to enroll individuals from the three groups that are targets for our formative evaluation activities, and study staff and team members will gather data from them in the ways described below:

*Interventionists.* We will conduct three recorded semi-structured video interviews with each interventionist. One will occur immediately after training; this will focus on their sense of the completeness and adequacy of the training program, including the training methods, videos, and materials, and their perceived readiness to lead the program. We will also interview them immediately after the conduct of each of the two Savvy programs they lead, asking them to report on their own performance as interventionists, including any adaptation processes in which they might have engaged, and to reflect on ways the training might be improved to strengthen their skills, including for adaptation. In total: 18 interviews.

*Savvy Participants.* Using an on-line survey method, we will ask each caregiver to complete the post-program fidelity monitoring survey (see Appendix) that seeks responses to the program (feel more knowledgeable, more competent, better equipped, etc.) and asks them to assess the interventionist's performance and verify that certain key elements of the program were covered (N=36; 6 in 6 groups). We will also conduct recorded semi-structured video interviews with a small sample of participants (N=8-12), selected to achieve maximum variability of relationship to care recipients, gender, racial/ethnic heritage, and rating of the program and the interventionists. Interviews will focus on caregivers' perceptions of the interventionist's

program leadership skills, any adaptation experiences, and on ways in which they met their own needs and expectations.

*Organizational Leaders.* We will conduct recorded semi-structured video interviews with sponsoring organizations' key contact persons immediately after the interventionist training and then after each of two Savvy offerings. The conversation will focus on identifying ways to strengthen and improve the training, certification, and fidelity monitoring system. We will also seek information about time and resource costs of the program, caregiver demand, and caregiver recruitment and feedback (3 interviews per organization).

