Results from Savvy participant quantitative fidelity monitoring surveys will be compiled in a simple spread sheet to allow us to see whether there are any notable problems in interventionist performance either within or across sites or in or across interventionists. Likewise, we will be able to compare caregivers' responses about knowledgeability and competence with responses we have received from other caregivers in Savvy programs provided by interventionists who were trained in person by [name] or [name].

Once a cohort of 20 consented caregivers has been formed at any local organization, participants will be assigned (through a random procedure administered by Emory staff) to take part immediately in one of the Savvy programs offered by either of the 2 interventionists or to take part in one of the 2 interventionists' programs after 4 months; follow-up phone or video interviews will be conducted at 2, 4, and 6 months lasting each 1-1.5 hours in length. The audio files from interviews will be saved on Emory School of Nursing's secure share-drive within a password protected folder for 5 years post-study completion.

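### Program-level clustering is left out of the standard errors: a small effect on the primary contrast, a larger one on the pooled paired t-test

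*Combined protocol and SAP*

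**What the plan says.** **Delivery.** "Six culturally or organizationally diverse sponsors will recruit 2 individuals each to be trained as Savvy interventionists (12 interventionists"), according to section 4. Under Field Methods, assignment takes place inside an organisation: "Once a cohort of 20 consented caregivers has been formed at any local organization", each caregiver goes at random either to immediate entry into "one of the Savvy programs offered by either of the 2 interventionists" or to one of their programs four months later. Section 3 gives 8-12 as the usual group size for Savvy in general. The only study-specific size is Aim 2's: "verify that certain key elements of the program were covered (N=36; 6 in 6 groups").

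**Analysis.** Section 10 plans mixed models "with random (participant) and fixed (cohort) effects will be employed". The primary comparison is immediate versus waitlist over 0m-2m. In addition, "the combined Savvy intervention effects will be assessed using a paired t-test", pooling the immediate arm's 0m-2m change with the delayed arm's 4m-6m change. Its only follow-on is an ANCOVA for differences just before treatment. Testing is at 5%. No program or interventionist term, organisation-by-time term, cluster-robust standard error or ICC is given.

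**Expected variation.** The fidelity surveys look for "any notable problems in interventionist performance either within or across sites or in or across interventionists", but only in a descriptive spreadsheet.

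**Use of the result.** If caregiver outcomes improve, section 10 says "this will provide a demonstration that system-trained interventionists can faithfully deliver Savvy", ahead of a Stage III or IV trial.

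**The concern.** Caregivers in the same program share a leader, that leader's local adaptations and their peers. Their changes under treatment may therefore be correlated. Caregivers still waiting share none of this. A participant random effect captures correlation between one person's visits, not between people in one program. The cohort effect does not help either, because each cohort contains both arms and a shift common to all its visits drops out of change. The planned standard errors thus assume that programs do not differ in the change they produce.

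In the primary contrast only the immediate arm is grouped. In the pooled test every change comes from a grouped, treated period, and there is no waiting arm to remove organisation differences. At stake is the precision claimed for the preliminary-efficacy evidence. The fidelity question, which section 10 calls central, is not affected.

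**Working it through.** **Stated figure.** 6 sponsors x 20 caregivers = 120, as in section 4. The documents give no power calculation, effect size, SD or ICC for Aim 3, so there is nothing further to reproduce.

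**Assumptions.** Two-sided testing; 1:1 allocation within each organisation (10 immediate, 10 delayed; 60 v 60); complete data; program ICC *p* of 0-0.10 and organisation share *o* of 0-0.05, both as fractions of the variance of change.

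**Program size *m*.** 10 immediate caregivers / 2 interventionists = 5. Aim 2's groups give 6. If all 10 entered one program, *m* = 10.

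**Does the cohort effect matter?** In one complete simulated data set, the SE of the group-by-time estimate was 0.2694 with a fixed cohort effect, 0.2694 without it, and 0.2694 from a t-test on change. It makes no difference.

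**Primary test, program variance only.** DEFF = 1 + (m - 1)p in the immediate arm and 1 in the waiting arm. True SE / planned SE = sqrt((DEFF + 1)/2). Type I error = 2 x P(t118 > critical value / SE ratio).

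| m | p | DEFF | SE ratio | Type I error |
|---|---|---|---|---|
| 5 | 0.01 | 1.04 | 1.010 | 5.2% |
| 5 | 0.02 | 1.08 | 1.020 | 5.5% |
| 5 | 0.05 | 1.20 | 1.049 | 6.2% |
| 6 | 0.05 | 1.25 | 1.061 | 6.4% |
| 10 | 0.05 | 1.45 | 1.107 | 7.6%-7.7% |

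Simulation (40,000 null trials per setting) gave 5.2%, 5.4% and 6.3% for m = 5 and 7.8% for m = 10, p = 0.05. At p = 0.10 the formula gives 7.3%-7.4% (m = 5) and 10.3%-10.4% (m = 10).

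**Primary test, organisations also differing in change (o = 0.05, m = 5).** The organisation effect is common to both arms, so it cancels from the difference but still enlarges each arm's sample variance.

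- True variance = (1 - p - o)/60 + p/12 + (1 - o)/60, with 12 immediate programs.
- Planned variance = the sum over arms of (1 - variance of that arm's mean)/59. The mean's variance is (1 - p - o)/60 + p/12 + o/6 in the immediate arm and (1 - o)/60 + o/6 in the waiting arm.
- p = 0: 0.0317 v 0.0331, SE ratio 0.978, type I error 4.5%.
- p = 0.02: 0.0330 v 0.0331, ratio 0.999, 5.0%.
- p = 0.05: 0.0350 v 0.0330, ratio 1.030, 5.7% (5.5%-5.8% in simulation).

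**Pooled test.** DEFF = 1 + (m - 1)p + 19o, with 20 caregivers per organisation. SE ratio = sqrt(DEFF), on 119 df. For m = 5:

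| p | o | DEFF | SE ratio | Type I error |
|---|---|---|---|---|
| 0.01 | 0 | 1.04 | 1.02 | 5.5% |
| 0.02 | 0 | 1.08 | 1.04 | 5.9% |
| 0.05 | 0 | 1.20 | 1.10 | 7.3% |
| 0 | 0.05 | 1.95 | 1.40 | 16% |
| 0.05 | 0.05 | 2.15 | 1.47 | 18% |
| 0.10 | 0.05 | 2.35 | 1.53 | 20% |

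Simulation agreed. A one-sample t-test on the six organisation mean changes held 4.8%-5.3% in all settings.

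**Schedule.** These sums use section 10's 0m-2m interval. Section 5 and Recruitment list no 2-month interview for the delayed arm, and they date its later interviews differently (from program start or from completion). Field Methods has 2, 4 and 6 months. These places must be reconciled. The variance ratios hold for any interval measured in both arms.

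**The case against.** The strongest reply is that the primary test is hardly affected. The 7.6%-7.7% figure needs all ten immediate caregivers in one program, whereas the wording about two interventionists points to about five each. A reader might infer that unmodelled clustering always makes the standard errors too small. It does not: with a 5% organisation share, programs of 5 and p = 0.02, the primary test sits at 5.0%. This objection stands and sets the size of the point.

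Second, the large pooled figures treat the six organisations as standing for a wider set, yet Recruitment describes purposive selection, partly through the team's contacts. If inference is limited to these six, the organisation part goes and only the program part remains. That also stands, but the plan states no target. Its conclusion about system-trained interventionists as a class points to the wider one.

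Third, the pooled test is an additional, uncontrolled comparison, and a better SE does not supply a concurrent control. That is true, but it does not justify an SE that ignores the grouping.

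Fourth, the parenthesis in section 10 may not list every model term, since group and time are missing from it too. An organisation-by-time term is therefore unstated rather than excluded. No wording supplies a program term, and a promise to test model assumptions does not commit to one.

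Finally, this is a Stage I project with unknown ICCs. That limits the stakes, but leaving the term out sets the ICC to zero.

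**Conclusion.** The point holds as a cheap improvement, and it is minor for the primary test. The missing program term is clear from the text; the size rests on assumed ICCs, organisation share and allocation.

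- **Primary 0m-2m contrast:** from no inflation to about 1.4 points above 5% for programs of 5-6 and ICC up to 0.05. The test can be slightly conservative if organisations also differ in change.
- **Pooled paired t-test:** about 0.5 to 2.3 points above 5% from program variance alone (programs of 5, ICC 0.01-0.05). It reaches about 16%-20% only with a 5% organisation share and inference beyond these six organisations.

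A reader might go further and infer that the primary result is unreliable, or that the primary model must carry an organisation-by-time term. The documents support neither. Randomisation is within organisation, so a shared organisation effect cancels from the primary contrast, and no such term is needed to prevent its inflation.

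**What to change.** In section 10:

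1. Keep participant random and cohort fixed. Add a random effect for Savvy program that acts only once that participant's program has started, with Satterthwaite degrees of freedom. An organisation-by-time term is optional, as a sensitivity analysis; if used, say whether time is a slope or categorical.
2. State the target of the combined analysis and replace the plain paired t-test. For wider inference, use a one-sample t-test on the six organisation mean changes, or a mixed model with both program and organisation acting on change. A program term alone still gave 10.2%-11.6% at a 5% organisation share (programs of 5). If inference is limited to these six, use a program-level term with organisation fixed.
3. Report the variance components with intervals and call them imprecise.
4. Reconcile the visit schedule across sections 5 and 10, Recruitment and Field Methods.

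**Cost.** SAP wording, plus a record of each caregiver's program. A version with both the program and a random organisation-by-time term was simulated on the two-point change with complete data. For programs of 5, primary intervals were 3%-11% wider and type I error was 4.1%-5.3%. At an assumed effect of 0.5 SD of change, power fell from 75%-78% to 69%-76%; part of that loss is inflation removed. Program variance was estimated at zero in 28%-65% of trials (programs of 5 or 10). The program term alone, the longer trajectories and attrition were not simulated, so these costs are a guide only.

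Pooled intervals on six organisation means are about 24% wider even without clustering. The critical values are 2.571 (5 df) and 1.980 (119 df), a ratio of 1.298. Multiplying by 0.952/0.998, the average ratio of sample SD to true SD with 6 and with 120 values, gives 1.24.
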